### **11.3.2.2 Secondary Endpoint Analyses**

Secondary endpoints will be analyzed for the ITT population only.

The analysis of secondary endpoints will use the same methodology as that for the primary endpoint analysis but adjusting for corresponding baseline value as a covariate. Treatment comparisons of 40 mg and 80 mg COR388 HCl to placebo for the secondary endpoints at 24-week or 48-week will be performed only if both co-primary endpoints compared to placebo are statistically significant. Otherwise, secondary endpoints will be presented using descriptive statistics

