##### Secondary Endpoints

Secondary endpoints in all subjects include:

- Change in Clinical Dementia Rating-Sum of Boxes (CDR-SB);
- Change in Mini-Mental State Examination (MMSE); and
- Change in Neuropsychiatric Inventory (NPI).

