## **11 STATISTICAL AND ANALYTICAL PLANS**

### **11.1 General Considerations**

The statistical analyses are described in this section. Further details will be provided in the Statistical Analysis Plan (SAP), which will be finalized prior to database lock and unblinding for the interim analysis. Any deviations from the analyses described below will be included in the SAP.

All efficacy and safety measures over the course of the study will be presented. Continuous data will be summarized by means, standard deviations (SDs), medians, maximum, minimum, and number of subjects. Categorical data will be summarized by counts and percentages.

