### **11.2 Determination of Sample Size**

The study will have an adaptive design that allows for potential adjustment in sample size and evaluation of efficacy based on the results of a planned interim analysis. An unblinded interim analysis will be conducted by a firewalled independent statistician (all clinical trial personnel will remain blinded) when approximately 100 subjects per arm have completed the Week 24 visit. Approximately 573 subjects are planned to be randomized 1:1:1 per treatment group (191 per treatment group) assuming approximately 10% will drop out prior to 48 weeks. Due to the planned interim analysis, adjustments will be made to the alpha level used in the final analysis to control for overall Type I error. The final criterion for efficacy to be used at the interim and final analysis depends on when the interim analysis occurs. The Lan-DeMets method modified according to [Chen et al. \(2004\)](#) to account for correlation between endpoints used at the interim and final analyses will be used to calculate the level of significance for each analysis. As originally planned, with 573 subjects randomized, an expected 10% discontinuation rate, and a single primary outcome, a total of 172 subjects per treatment group would provide approximately 90% power to detect a 2.5-point difference between the active treatment group compared to placebo with respect to change from baseline on the ADAS-Cog 11, assuming a standard deviation of 7.1, respectively at a significance level (alpha) of 0.05 using a two-sided test. The ADCS-ADL was added as a co-primary outcome, with assumptions of a 3.9-point difference between the active treatment group compared to placebo with respect to change from baseline on ADCS-ADL, assuming a standard deviation of 10.5, providing approximately 95% power on this outcome

measure, with approximately 90% power for the overall co-primary outcomes, depending on their correlation.

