These results assume that 2 sequential tests will be made using the Lan-DeMets spending function to determine the test boundaries. Therefore, if an interim analysis is conducted when approximately 300 subjects have completed the Week 24 visit, then a significance level of 0.005 will be used for the interim analysis and a significance level of approximately 0.0456 will be used for the final analysis. As discussed by [Chen et al 2004](#), the sample size re-estimation procedure based on promising zone will not inflate the type I error and no statistical adjustment is necessary. However, the adjusted alpha at the end of the study will be based on the new sample size at the final analysis.

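### If the co-primary gate closes at the final analysis, the plan withholds the secondary-endpoint comparisons themselves, not only the claim of significance

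*Protocol*

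**What the plan says.** - **Model.** Protocol Section 11.3.2.2: "The analysis of secondary endpoints will use the same methodology as that for the primary endpoint analysis", with the endpoint's own baseline value as covariate. Section 11.3.2.1 defines that model as an MMRM with terms for site/country, baseline MMSE, ApoE4 status and background symptomatic therapy.
- **Gate.** The same section says that dose-versus-placebo comparisons for "secondary endpoints at 24-week or 48-week will be performed only if both co-primary endpoints compared to placebo are statistically significant". Section 11.3.2.3 repeats the rule with levels of about 0.005 (interim) and 0.0456 (final).
- **If the gate is closed.** "Otherwise, secondary endpoints will be presented using descriptive statistics". Section 11.3.2.3 says the same.
- **What a summary contains.** Section 11.1: "Continuous data will be summarized by means, standard deviations (SDs), medians, maximum, minimum, and number of subjects".
- **Related provisions.** The secondary endpoints are CDR-SB, MMSE and NPI (Section 4.1.2). Section 11.3.5 makes CDR-SB at Week 24 an interim co-primary. The sensitivity analyses of Section 11.3.2.1.1 cover the co-primaries only. Section 11.3.2.4 states no gate for exploratory endpoints.

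**The concern.** A gate that protects Type I error has to restrict claims. It does not have to restrict estimation. Here the rule decides whether the comparison is performed at all, so a closed gate replaces a specified model-based estimate with arm-level summaries.

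The secondary endpoints matter most for interpretation when the co-primaries split, for example when ADAS-Cog 11 is positive and ADCS-ADL narrowly misses. Readers would then want the Week 48 CDR-SB difference and its precision. They would be left to subtract raw means, which use only the subjects still observed and ignore every covariate the protocol chose for the model. As written, the exploratory endpoints would be less restricted than the secondary ones.

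**Working it through.** **1. The plan's own power figures.** Inputs from Section 11.2: 172 evaluable per arm; ADAS-Cog 11 difference 2.5, SD 7.1; ADCS-ADL difference 3.9, SD 10.5; two-sided alpha 0.05. Power = Φ(δ/(SD·√(2/n)) − 1.96), with √(2/172) = 0.1078.
- ADAS-Cog 11: 2.5/(7.1 × 0.1078) = 3.27, giving 0.904. Stated: about 90%.
- ADCS-ADL: 3.9/(10.5 × 0.1078) = 3.44, giving 0.931. Stated: about 95%, which is what 191 per arm gives (0.953).

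**2. How often the gate closes for one dose.** At 0.0456 the two powers are 0.897 and 0.926. The correlation between endpoints is not given. If it is 0, joint power is 0.8973 × 0.9258 = 0.831; if it is 0.9, joint power is 0.881. One dose that works exactly as assumed therefore misses the gate in 12-17% of trials before any adjustment for two doses. The protocol's own overall figure of about 90% implies about 10%.

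**3. With both doses.** Simulation of three arms and two endpoints, 172 per arm, Benjamini-Hochberg across doses within each endpoint at 0.0456, 400,000 runs, same true effect in both doses. Ranges cover an assumed endpoint correlation of 0 to 0.7.

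| True effect, both doses | A given dose fails | Both doses fail |
|---|---|---|
| Full design effect | 15-19% | 8-10% |
| Half | 79-90% | 71-84% |
| None | over 99% | over 99% |

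The text does not say whether the gate works dose by dose or needs both doses. If it needs both, it closes in 23-28% of trials even at the full effect (chance that both pass: 0.724 to 0.775).

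**4. What is lost.** With 172 per arm, a nominal 95% interval for each dose-placebo difference has a half-width of 1.96 × √(2/172) = 0.21 SD. The protocol gives no SDs for the secondary endpoints, so this stays in SD units. Leaving out a baseline covariate that has correlation r with the outcome multiplies the variance by 1/(1 − r²): 1.10 at r = 0.3 and 1.33 at r = 0.5 (both values of r assumed).

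**5. Raw means under dropout (illustration only).** Two assumed mechanisms:
- *Dropout depends on earlier decline in both arms.* With equal dropout the bias of the raw Week 48 difference is about 0. With 10% on placebo against 20% on active it is 0.026-0.067 SD.
- *Placebo dropout 10% at random; active dropout related to Week 24 worsening; Week 24-Week 48 correlation 0.7; true difference −0.30 SD.* Raw difference: −0.38 (10% active dropout, odds ratio 4 per SD), −0.39 (20%, odds ratio 2), −0.45 (20%, odds ratio 4). The MMRM-type estimate is −0.30 in all three.

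At equal dropout rates the two mechanisms give about 0 and 0.08 SD. The result is set by the assumed mechanism, not by anything in the protocol.

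**The case against.** **The wording may allow more.** The statement of the secondary model carries no condition, the gate speaks only of treatment comparisons, and descriptive statistics could be read to include model-based means. Section 11.1 also leaves details and deviations to the SAP, which is not at hand. Part of this stands: the SAP may report nominal estimates. But the protocol states a rule, twice, and does not merely leave a gap. An SAP that reported the MMRM differences after a closed gate would depart from it.

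**The gate is conventional and conservative.** This stands. Nothing here shows a Type I error problem, and the gate should remain for claims.

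**Nothing is irretrievably lost.** The data are collected in any case. A reader could form a crude difference from means, SDs and n, and the model could be fitted later. True, but the first is unadjusted and the second would be post hoc.

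**Stronger readings that do not hold.** A reader might infer that CDR-SB would never be compared with placebo. Section 11.3.5 contradicts this: both doses are compared at Week 24 at the interim, outside this gate. That comparison, planned at about 300 subjects, does not supply the Week 48 estimate. A reader might also infer that the raw means will favour the drug. The protocol gives only about 10% dropout overall. Its visible route to unequal dropout is safety stopping (Sections 8.24 and 12.13), which it does not link to cognitive decline. Dropout unrelated to outcome gives no such bias, and heavier loss of fast decliners on placebo would reverse the sign.

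**Conclusion.** The point holds for the final analysis: with the gate closed, the plan as written gives no adjusted Week 48 difference and no interval for CDR-SB, MMSE or NPI, while specifying the model that would provide them. This follows from the text and needs no assumption about dropout.

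The closed-gate branch is a realistic reporting path: about 8-10% of trials for both doses together at the full design effect, and most trials if the effect is half as large. These figures assume 172 per arm, equal effects in both doses and an endpoint correlation of 0 to 0.7.

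The bias figures show only that raw means can mislead where a model-based estimate would not; they do not predict a size or direction in this trial. The primary inference, alpha and sample size are unaffected. This is a worthwhile, inexpensive correction to a reporting rule, not a threat to the trial's confirmatory conclusion.

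**What to change.** Replace the closed-gate sentence in Sections 11.3.2.2 and 11.3.2.3 with wording such as:

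> The MMRM will be fitted to CDR-SB, MMSE and NPI in all cases, and the adjusted difference from placebo for each dose at Weeks 24 and 48 will be reported with a nominal 95% CI. If the gate is not passed, these results are labelled descriptive and no claim of statistical significance is made.

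All three scales are scheduled at both weeks (Table 1), and the model is already specified. The change costs two sentences per section, spends no alpha, and needs no extra subjects or data. Its one drawback is that nominal intervals may be over-read after a missed co-primary, which the label is there to prevent.

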### **11.3.2.3 Multiplicity**

To control for type I error, for the interim and final analysis will be adjusted using the Lan-DeMets spending function. If the study does not stop at the interim analysis (i.e., 24 weeks ADAS-Cog and CDR-SB as co-primary endpoints) for overwhelming efficacy or futility, the study will retain its original design and the final analysis will be based on 48 weeks of treatment with ADAS-Cog and ADCS-ADL as co-primary endpoints. Because of the changes in co-primary endpoint at 48 weeks (i.e., CDR-SB 24-week replaced by ADCS-ADL at 48-week and ADAS-Cog 24-week replaced by ADAS-Cog 48-week), the Lan-DeMets correction for sequential analysis will be further adjusted as described in [Chen et al., \(2014\)](#). This adjustment will account for the correlation between the outcomes and time points. The boundaries will be calculated to account for the change in timing of evaluation and endpoint and the more conservative boundary will be used for final analysis at 48-week.

At both the interim analysis at 24 weeks and final analysis at 48 weeks, to adjust for comparison between placebo and each of the two doses, Benjamini-Hochberg multiplicity adjustment procedure ([Benjamini and Hochberg, 1995](#) and [Benjamini and Yekutieli, 2001](#)) will be used. Both treatment comparisons, 40 mg (low dose) and 80 mg COR388 HCl (high dose) to placebo are considered of equal interest.

Treatment comparisons of 40 mg and 80 mg COR388 HCl to placebo for the secondary endpoints at 24-week or 48-week will be performed only if both co-

primary endpoints compared to placebo are statistically significant at the level of approximately 0.005 or 0.0456 for the interim analysis and final analysis, respectively. Otherwise, secondary endpoints will be presented using descriptive statistics.

#### **11.3.2.4 Exploratory Endpoints**

Exploratory endpoints will be analyzed for the ITT population only. No adjustment for multiplicity will be done.

Further details of the analyses to be performed will be provided in the SAP.

### **11.3.3 Safety Analysis**

#### **11.3.3.1 Adverse Events**

Adverse events will be coded by Preferred Term (PT) using the Medical Dictionary for Regulatory Activities (MedDRA) classification.

A treatment-emergent adverse event (TEAE) is defined as any AE that has an onset on or after the first dose of study drug, or any pre-existing condition that has worsened on or after the first dose of study drug. The incidence of TEAEs, treatment-related TEAEs, SAEs including deaths, TEAEs that lead to discontinuation of investigational product, and TEAEs by maximum severity and relationship to study drug will be summarized by MedDRA system organ class, PT, and treatment group.

To assess the potential for abuse associated with the administration of COR388 HCl, a systematic review of TEAE terms suggestive of the potential for abuse will be conducted for all clinical studies in subjects who received at least 1 dose of COR388 HCl and a summary of this information will be included in the regulatory submission. As a general framework for data collection and analysis we will use the overall abuse flag terms in the FDA Guidance (2017).

Since the target patient population are elderly, have substantial comorbidity and are often on other medications, a careful assessment and documentation of adverse event causality will be made in order to ensure that false positive TEAE signals for abuse are not generated. For example, dizziness and sedation or sleepiness are common clinical events in elderly patients with Alzheimer's disease.

Since to date no abuse related TEAE attributable to COR388 HCl have occurred, focus will be on a restricted set of index events for which narratives will only be prepared where the causality relationship to COR388 HCl is probable or definite. Information included in the narratives will consist of time to onset/offset, time course of severity, all concurrent events, concurrent medications, and time of onset of events relative to ingestion of COR388 HCl.

The index TEAEs will include:

- Any reports of altered perception or hallucinations
- Dizziness
- Euphoric mood
- Feeling drunk
- Feeling of relaxation
- Sedation
- Somnolence

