## **9 ADVERSE EVENT REPORTING**

Throughout the course of the study, all adverse events (AEs) will be monitored and recorded on an AE eCRF, including the AE's description, start and end date, seriousness, severity, action taken, and relationship to the investigational product. If AEs occur, the first concern will be the safety of the study subjects. All AEs will be followed until resolved or stable and the outcome documented on the eCRF.

Open Label Extension: Adverse events will be monitored at all visits and phone calls. **NOTE:** Effective 16 February 2021, the OLE portion of the study was terminated by the Sponsor.

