#### **Relationship**

Each AE will be assessed as to its relationship to the investigational product, based on the following criteria. Although the attribution by the Investigator will be collected for reported events, for analytic purposes a temporal association with the use of the investigational product will be assumed sufficient for at least plausible association.

- Not related: No causal relationship exists between the investigational product and the AE, but an obvious alternative cause exists, e.g., the subject's underlying medical condition or concomitant therapy.
- Possibly related: A connection with the administration of the investigational product appears unlikely but cannot be ruled out with certainty. An AE may be considered possibly related if or when it meets 2 of the following criteria: (1) it follows a reasonable temporal sequence from administration of the investigational product; (2) it could not readily have been produced by the subject's clinical state, environmental or toxic factors, or other modes of therapy administered to the subject; or (3) it follows a known pattern of response to the investigational product.
- Related: There is a reasonable/plausible possibility that the AE may have been caused by the investigational product.

When assessing the relationship to the investigational product, the following criteria will be considered:

- Positive re-challenge (restart of IP dosing following dosing interruption);  
Note: In this study re-challenge of IP will not be allowed if IP dosing was discontinued for IP-related safety reasons e.g. when a DILI protocol is triggered and/or due to an AE that was assessed as possibly or probably related to the IP.
- Positive de-challenge (resolution upon stopping suspect the investigational product, in absence of other intervention or treatment);
- Known class effect;
- Biological plausibility; and
- Lack of alternative explanation—concomitant drug or disease.

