## 9.2 Reporting Procedures and Requirements

### 9.2.1 Adverse Events

Adverse events (AEs) occurring from when the subject signs the ICF until the last study event will be recorded. Any AEs occurring before the start of treatment (i.e., before the first dose of the investigational product) will be recorded in the medical

history. Also, the sign, symptom, or disease present before starting the treatment period are only considered AEs if they worsen after starting the treatment period.

If the Investigator detects an AE in a study subject after the last scheduled follow-up visit and considers the event possibly related or related to prior study treatment, the Investigator should report it to the Sponsor/ Contract Research Organization (CRO).

The Investigator should report all AEs on the AE page(s) of the eCRF and source documents, regardless of seriousness, severity, and causality. Whenever possible, an AE will be reported using a diagnostic term, (e.g., “common cold” or “upper respiratory infection” rather than “runny nose, cough, mild fever”) and should be described with the attributes described in [Section 9.1.5](#).

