### **9.2.2 Serious Adverse Events**

Each AE will be assessed to determine whether it meets seriousness criteria ([Section 9.1.2](#)). If the AE is considered serious, the Investigator should report this event to the Sponsor and CRO as outlined below and also to the IRB/IEC according to its standard operating procedures.

If the Investigator detects an SAE in a study subject after the last scheduled follow-up visit, and considers the SAE related or possibly related to prior study treatment, the Investigator should report it to the Sponsor and CRO.

All information about SAEs will be collected and reported via the SAE form and sent by e-mail message or facsimile (contact information will be contained in the Investigator site file). The Investigator should send the initial report within 24 hours of becoming aware of the SAE. At minimum, the initial report should include the following information:

- Event;
- Study code;
- Subject number, initials, and date of birth;
- Investigational product; and
- Reporter name and contact information.

In the case of a “minimum report” (one that solely comprises the information bulleted above), a more detailed follow-up report should be sent as soon as more information becomes available, but no later than 7 calendar days after the date of the initial report. Each SAE should be followed up until resolution or stabilization and for reported deaths, the Investigator should supply Sponsor/ CRO and the IRB/IEC with any additional requested information (e.g., autopsy reports and terminal medical reports).

The original SAE form should be kept at the study site. The Sponsor or its representative will be responsible for determining and in turn, reporting SAEs to regulatory authorities according to the applicable regulatory requirements.

Serious adverse events that are ongoing at Safety Follow-up Visit 11 of OLE-9 should be followed until resolved or stabilized.

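### Does the abuse-narrative trigger in Section 11.3.3.1 need changing because it names causality grades that the protocol's scale does not contain?

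*Protocol*

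**What the plan says.** Section 9 of the protocol has the adverse event eCRF record, among other items, "seriousness, severity, action taken, and relationship to the investigational product". Section 9.1.5, under Relationship, defines the grades. Below the top grade and above Not related stands "Possibly related: A connection with the administration of the investigational product appears unlikely but cannot be ruled out with certainty". That definition goes on to allow the grade when two of three criteria hold: plausible timing, no ready alternative explanation, or a known response pattern. The top grade reads "Related: There is a reasonable/plausible possibility that the AE may have been caused by the investigational product".

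The same section adds that "for analytic purposes a temporal association with the use of the investigational product will be assumed sufficient for at least plausible association". Its note on re-challenge gives, as one example, dosing discontinued "due to an AE that was assessed as possibly or probably related to the IP".

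Sections 9.2.1 and 9.2.2, on events found after the last follow-up visit, keep to the defined labels: "considers the event possibly related or related to prior study treatment" and "considers the SAE related or possibly related to prior study treatment".

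Section 11.3.3.1 plans TEAE tables, including tables by relationship, and a review of abuse-suggestive terms across all clinical studies of COR388 HCl. It calls for careful causality assessment so that false abuse signals are avoided. It then narrows attention to seven index event types and states that "narratives will only be prepared where the causality relationship to COR388 HCl is probable or definite".

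**The concern.** The trigger is exclusive and is written in two words, probable and definite, that name no grade on the trial's scale. If the Investigator's recorded grade is the input, nothing recorded can satisfy it and the abuse-potential narratives would be empty by construction. Someone must then choose a substitute, and the choice is not automatic. The top grade asks only for a plausible possibility, which is looser than probable. The temporal-association sentence in Section 9.1.5 could be read as looser still.

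The abuse review is to be summarised in a regulatory submission. A selection rule that has to be interpreted after the event could therefore look as if it had been chosen with knowledge of the results.

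**Working it through.** No arithmetic beyond counting labels applies, so the check sets the places side by side.

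| Place in the protocol | Causality labels used | On the Section 9.1.5 scale? |
|---|---|---|
| 9.1.5, definitions | Not related, Possibly related, Related | This is the scale |
| 9.1.5, re-challenge note | possibly, probably | First yes, second no |
| 9.2.1 | possibly related, related | Yes |
| 9.2.2 | related, possibly related | Yes |
| 11.3.3.1, narrative trigger | probable, definite | Neither |

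**Step 1: size of the mismatch.** Grades on the scale: 3. Grades labelled probable or definite: 0. Places with an off-scale causality word: 2 (the re-challenge note and the narrative trigger).

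**Step 2: can the trigger be mapped to the scale?** Related is the nearest grade, though not an exact match, since it requires only a plausible possibility. Possibly related pulls two ways. Its opening calls a connection unlikely, but an event with plausible timing and no ready alternative explanation also qualifies for it. The text therefore points towards Related without settling the matter.

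**Step 3: is the Investigator's grade the intended input?** Section 11.3.3.1 does not say. In favour: relationship is on the eCRF, and the protocol defines no other scale. Against: the section speaks of its own causality assessment, for a review that covers every clinical study of the drug. Wording taken from a programme-level text would explain the different labels. The conclusion that no narrative could ever be written holds only under the first reading.

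**Step 4: range of outcomes.** Under the literal reading with the Investigator's grade, there are no narratives. If Related is taken as the trigger, narratives cover the index events given that grade. If the temporal rule selected narratives, they could cover many more index events, which sits badly with the section's aim of a restricted set. The protocol gives no counts of index events by grade, so none of these can be turned into a number.

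**Step 5: what depends on the trigger.**

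- TEAE incidence by system organ class and preferred term: no. Index events reported as TEAEs appear there whether or not a narrative exists.
- TEAE tables by relationship: no. They do not pass through the narrative trigger.
- Review of abuse-suggestive terms: no. It selects on the event term.
- Efficacy estimates and tests: no.
- Descriptive narratives for the 7 index event types (altered perception or hallucinations, dizziness, euphoric mood, feeling drunk, feeling of relaxation, sedation, somnolence): yes, and nothing else.

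**Step 6: can the gap bias the comparison of arms?** Section 5.4.3 keeps Investigators blinded through Visit 11 apart from emergency unblinding, so grades are assigned without knowledge of treatment in the ordinary course. No table or test is filtered by the narrative choice.

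**The case for a change.** The best case for a change is that this is a misstatement and not merely an omission. The protocol fixes a trigger with the word only and then uses labels that its own scale lacks. An SAP could work around that but would not make the protocol sentence right. The re-challenge note shows that it is not a single typing error. The repair would cost one phrase and no data, and a rule fixed before unblinding is easier to defend in a submission than one settled later. Narratives are also meant to give onset relative to ingestion, while Section 9 lists start and end dates for adverse events, so some detail may be harder to recover for a narrative written late.

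Much of this stands. The labels do conflict, and fixing a rule early is good practice. What does not stand is the inference that something is lost without a change. The recorded grade survives whatever rule is chosen, and every reported index event remains visible in the TEAE tables. The point about time of onset concerns which details are collected for an event and would arise under any trigger.

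The obvious repair is not neutral either. Writing Related into the sentence replaces a probable-or-definite threshold with a plausible-possibility one, which widens a set that the section wants kept narrow. The text does not dictate that choice.

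**Conclusion.** No change to the plan follows. Sections 9.1.5 and 11.3.3.1 use different causality vocabularies, with 0 of 3 defined grades carrying a trigger label. The consequence stops at which descriptive narratives are written for seven index event types. No estimate, test, table or term review moves, no bias between arms arises, and a narrative left out can be written later from recorded data. The team preparing the abuse review will have to say which causality rating it used and at what level. That is ordinary practice, and Section 11.1 leaves further analysis detail to the SAP in any case.

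This rests on three assumptions: that relationship is captured on the eCRF in the three defined grades, that the trigger governs narratives and nothing else, and that the safety team reads it sensibly and does not take it as an instruction to write none.

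The re-challenge note touches clinical management. On that I say only that its wording and the defined grades in Section 9.1.5 do not match and must be reconciled by those responsible for the clinical text. I take no position on which rule is right, and the note has no bearing on the statistical analysis.
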